3.2.23 Patients on medications known to be associated with Torsades de Pointes

- 3.2.24 Patients who received the last administration of an anti-cancer therapy including, chemotherapy, immunotherapy/biologic therapy, targeted therapy or radiotherapy within 4 weeks (6 weeks for nitrosoureas or mitomycin C) or within 5 half-lives, whichever is shorter, prior to entering the study.
- 3.2.25 Patients who have not recovered (\leq CTCAE grade 1) from adverse events (with the exception of alopecia) due to agents administered more than 4 weeks earlier.
- 3.2.26 Patients taking medications or herbal supplements that are known to be strong CYP3A4 inhibitors within at least 14 days prior to registration are excluded
- 3.2.27 Patients with symptomatic or progressive brain metastases are ineligible. Subjects with treated brain metastases are eligible if they have no radiographic or other signs of progression in the brain for \geq 4 weeks after completion of local therapy.
- 3.2.28 Patients with macular edema, retinal vein occlusion or retinal hemorrhage are excluded.
- 3.2.29 Patients who have received prior FGFR targeted therapy.

3.3 Inclusion of Women and Minorities

Both men and women of all races and ethnic groups are eligible for this trial. It is expected that the patients entering this study will reflect the demographics of our clinical population and geographic area. We expect that some participants will be racial/ethnic minorities which reflects the catchment area.

4. REGISTRATION PROCEDURES

4.1 General Guidelines

Eligible patients will be entered on study centrally at the *The Ohio State University*. OSU patients will be registered by the OSU Clinical Research Specialist/Coordinator. External participating site patients will be registered by the OSU Multi-Site Coordinator. External sites should alert the Multi-Site Coordinator by e-mail or phone as soon as a potential patient is identified for screening. The required registration forms can be found in the protocol Supplemental Forms packet.

Following registration, patients should begin protocol treatment within 5 business days. Issues that would cause treatment delays should be discussed with the Principal Investigator. If a patient does not receive protocol therapy following registration, a written explanation documenting the reason for delay will be required before proceeding with therapy. The Multi-Site Coordinator should be notified of any cancellations as soon as possible. The patient's registration may be cancelled, pending approval by the Principal Investigator who will determine whether the patient will be replaced.

4.2 External Participating Site Registration Process

External participating site patients will have eligibility verified and will be centrally registered at The Ohio State University by the OSU Multi-Site Coordinator. Participating sites should call or email the OSU Multi-Site Coordinator to verify enrollment availability prior to consenting patients.

Following registration, patients should begin protocol treatment within 5 business days. Issues that may cause treatment delays should be discussed with the OSU Principal Investigator and OSU Multi-Site Coordinator as soon as possible. The OSU Multi-Site Coordinator must be notified immediately if a patient does not receive protocol therapy.

Only patients deemed eligible by the participating site research team should be submitted for eligibility verification and registration by the OSU Multi-Site Coordinator.

To request patient registration, the documents below must be completed by the participating site research team and faxed to the OSU Multi-Site Coordinator. The OSU secure e-mail system may be used, if needed. Contact the OSU Multi-Site Coordinator for more information. Regular e-mail must not be used to send patient registration documents.

Required documents for registration:

- Enrollment Form (refer to Supplemental Forms packet)
- Signed Eligibility Checklist (refer to Supplemental Forms packet)
- Signed informed consent document (and HIPAA if separate form)
- Documentation of consent process
- Source documents verifying every inclusion & exclusion criteria
- Source documents for every required screening item as listed in the Protocol Calendar. Screening tests must be within the specified window.
- Other signed and dated documents used as source documentation

The OSU Multi-Site Coordinator will confirm receipt of the registration documents with the participating site contact listed on the Enrollment Form. If confirmation is not received within 2 hours, it is strongly recommended that the participating site call the OSU Multi-Site Coordinator to confirm registration documents were received.

Registration requests will be processed as soon as possible and no later than 1 business day after receipt of the registration documents, pending there is no additional information needed to complete eligibility verification. Registration will occur upon OSU confirmation that the patient meets eligibility criteria.

The Multi-Site Coordinator will securely email the participating site contact listed on the Enrollment Form with the registration confirmation and the patient's assigned study number.

5. TREATMENT PLAN

5.1 Agent Administration

Ponatinib would be administered as a single agent at a starting dose of 45 mg oral once daily on an outpatient basis. In clinical trials involving CML and ALL the starting dose of ponatinib was 45 mg administered orally once daily. However, 59% of the patients required dose reductions to 30 mg or 15 mg once daily during the course of therapy. The optimal dose of ponatinib in solid tumors has not been identified. All subjects should receive a copy of the Ponatinib Medication Guide (Appendix D).

Reported adverse events and potential risks are described in **Section 7**. Appropriate dose modifications are described in **Section 6**. Details regarding administration of study drugs are detailed in **Section 8**. No investigational or commercial agents or therapies other than those described below may be administered with the intent to treat the patient's malignancy. The patient will be requested to maintain a medication diary of each dose of medication. The medication diary will be returned to clinic staff at the end of each course.

Ponatinib at a dose of 45 mg should be taken orally once daily with or without food for a 28 day cycle. Tablets should be swallowed whole. Patients should not crush or dissolve the tablets. Continue treatment as long as the patient does not show evidence of disease progression or unacceptable toxicity (**Section 5.3**).

Patients treated with ponatinib are recommended to have concomitant thrombo-prophylaxis with ASA (81 or 325 mg daily), if tolerated. Patients with documented allergy to aspirin do not require an alternate agent and are still eligible. ASA should be held when platelets drop to 75000 or below.

5.3 Duration of Therapy

In the absence of treatment delays due to adverse event(s), treatment may continue until one of the following criteria applies:

- Disease progression,
- Unacceptable adverse event(s)
- Intercurrent illness that prevents further administration of treatment,
- Patient decides to withdraw from the study, or
- General or specific changes in the patient's condition render the patient unacceptable for further treatment in the judgment of the investigator.

5.4 Duration of Follow Up

Patients will be followed every 3 months for 52 weeks after removal from study or until death, whichever occurs first, in order to document time of progression (if patient did not progress while on study), survival, and to document subsequent alternate therapy received. Patients removed from study for unacceptable adverse event(s) will be followed until resolution or stabilization of the adverse event.

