5.5 Criteria for Removal from Study

Patients will be removed from study when any of the criteria listed in **Section 5.3** applies. The reason for study removal and the date the patient was removed must be documented in the Case Report Form.

Patients must be discontinued from the trial in the event of myocardial infarction, stroke,

development or progression of arterial disease necessitating revascularization, or other vascular occlusive events.

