5. Including alkaline phosphatase, total bilirubin, albumin, creatinine, glucose, potassium, SGOT, SGPT, sodium, magnesium, chloride, bicarbonate, phosphate.
6. Perform only in women of child-bearing potential.
7. Research biopsies will be performed as part of the OSU Precision Cancer Trial (or through MI-ONCOSEQ for study enrollment at University of Michigan). Blood, buccal samples must also be obtained per **Section 9**.
8. Radiologic documentation must be provided for patients removed from the study due to progressive disease for solid tumors. CT chest/abdomen/pelvis is preferred. Bone scan, MRI or PET may be used at the discretion of treating physician.
9. Patients discontinuing for toxicity are followed until resolution of the toxicity, as outlined in **Section 5.4**. Patients who have discontinued protocol therapy will be followed every 3 months for 52 weeks or until death, whichever occurs first, in order to document time of progression (if patient did not progress while on study), survival, and to document subsequent alternate therapy received. For patients with resolution of toxicity to protocol therapy, telephone follow-up is permitted.

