12. STATISTICAL CONSIDERATIONS

12.1 Study Design/Endpoints

With the advent of genomic profiling and targeted therapies, focusing on patients with a specific target (or genomic alteration) of interest regardless of disease type or histology is a new paradigm that cancer research is beginning to adopt. This is a Phase-2, "basket" study for patients with advanced cancers (stage 4, any histology) who have disease progression with at least one prior regimen, identified with predefined genomic alterations. Two separate cohorts will be accrued in parallel, defined by genomic *FGFR*, as well as *KIT*, *PDGFR α* , *ABL1*, *RET*, and *FLT3* alterations.

Cohort A will consist of patients identified with activating mutations or fusions in *FGFR* as well as patients with *FGFR* amplifications.

Cohort B will consist of patients identified with rare gene targets (*KIT*, *PDGFR α* , *RET*, *ABL1*, and *FLT3* alterations) for whom there may be downstream targeting and efficacy associated with ponatinib.

Our goal is to assess efficacy outcomes in these two cohorts when treated with ponatinib.

(a) Definition of primary outcome/endpoint:

The primary endpoint for each of the cohort in this study is overall response. Overall response is defined as the number of patients who achieve any response in the first 6 cycles of treatment. All eligible patients, selected by a CLIA approved assay, who have received at least one dose of ponatinib will be evaluable for response. Response for tumors would be assessed using the RECIST 1.1 criteria (using CT scans or calipers by clinical exam) where response will be defined as a partial or complete response.

(b) Definition of secondary outcomes/endpoints:

- Toxicity is defined as adverse events that are classified as either possibly, probably, or definitely related to study treatment per NCI CTCAE v4.0
- Overall survival is defined as the time from treatment initiation to death.
- Progression-free survival defined as the time from treatment initiation to progression or death

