12.4 Analysis of Secondary Objectives

- Frequency and severity of adverse events and tolerability of the regimen will be collected and summarized by descriptive statistics. As per NCI CTCAE v4.0, the term toxicity is defined as adverse events that are classified as either possibly, probably, or definitely related to study treatment. The maximum grade for each type of toxicity will be recorded for each patient, and frequency tables will be reviewed to determine toxicity patterns for each of the cohorts as well as across cohorts. In addition, we will review all adverse event data that is graded as 3, 4, or 5 and classified as either “unrelated” or “unlikely to be related” to study treatment in the event of an actual relationship developing. The incidence of severe (grade 3+) adverse events or toxicities will be described. We will also assess tolerability of the regimen through

assessing the number of patients who required dose modifications and/or dose delays. In addition, we will capture the proportion of patients who go off treatment due to adverse reactions or even those who refuse further treatment for lesser toxicities that inhibit their willingness to continue participation on the trial. All patients who have received at least one dose of any of the therapeutic agent will be evaluable for toxicity and tolerability.

- Overall and Progression Free Survival as time-to-event outcomes. Kaplan-Meier curves will be used to estimate the survival distributions of overall survival and progression-free survival for each cohort. Each of these variables is measured from the date of study registration to the date of event (ie, death and/or disease progression) or the date of last follow-up if no event has occurred.
- Clinical benefit rate (CBR) at 6 months. The 6-month CBR will be calculated by the number of patients who have achieve a response and/or are progression-free and alive at 6 months divided by the total number of evaluable patients. Exact binomial 95% confidence intervals for CBR will be calculated.

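### Overall-survival follow-up ends 52 weeks after each patient stops ponatinib, so the Kaplan-Meier curve beyond about 12 months is subject to informative censoring, probably but not certainly upward

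*Combined protocol and SAP*

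**What the plan says.** Section 5.4: "Patients will be followed every 3 months for 52 weeks after removal from study or until death, whichever occurs first". Recording survival is one of its stated purposes. Footnote 9 to the section 10 calendar gives the same period, counted from the end of treatment: "Patients who have discontinued protocol therapy will be followed every 3 months for 52 weeks or until death, whichever occurs first". It adds that, once toxicity has resolved, "telephone follow-up is permitted".

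The two starting points coincide, because section 5.5 says "Patients will be removed from study when any of the criteria listed in" section 5.3 applies, and section 5.3 lists the reasons for ending treatment. These are progression, unacceptable adverse events, intercurrent illness, withdrawal, and the following: "General or specific changes in the patient's condition render the patient unacceptable for further treatment in the judgment of the investigator".

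Section 12.1: "Overall survival is defined as the time from treatment initiation to death". Section 12.4: "Kaplan-Meier curves will be used to estimate the survival distributions of overall survival and progression-free survival for each cohort". Patients are censored at the date of event "or the date of last follow-up if no event has occurred". The documents give no common OS cut-off date, no longer survival follow-up, no time at which the curve is truncated, and no method for dependent censoring.

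**The concern.** Kaplan-Meier assumes that a patient censored at a given time has the same later risk of death as patients still under observation then. Here the limit of observation is fixed by when treatment stopped. After about a year, patients who stopped early and are still alive leave the risk set. Their later deaths are not seen, and patients who stayed on ponatinib longer stand in for them.

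If early stopping marks a worse prognosis, the later part of the OS curve sits too high. OS is a stated secondary objective (section 1.2), and section 12.4 plans a curve per cohort with no stated end. In a single-arm trial no control curve affected by the same rule is there to warn the reader.

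**Working it through.** **The plan's own figure.** There is none to reproduce. The documents state no expected OS, progression-free survival, time on treatment or event count.

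**Censoring time from the text.** Let D be time on ponatinib and R survival after stopping. OS is T = D + R, and the latest observation is C = D + 52 weeks, where 52 × 7 / 30.4375 = 11.96 months.

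- Stopping at the first 8-week scan: 8 + 52 = 60 weeks, or 60 × 7 / 30.4375 = 13.8 months.
- Appendix E says some patients may be on therapy for 6 to 30 months: 6 + 11.96 = 18.0 and 30 + 11.96 = 42.0 months.

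Observation limits thus run from about 14 to 42 months according to time on drug. Since C cannot be below 11.96 months, the rule itself censors nobody before week 52.

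**Simulation.** Assumptions, none from the documents: median D 2 to 6 months, median R 4 to 12 months, 400,000 patients per scenario. Kaplan-Meier OS under the rule was compared with true OS.

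*Shared prognosis.* D and R are exponential with a shared gamma frailty of variance 0.25, 0.5 or 1.0, with and without 20% early toxicity stops unrelated to prognosis (24 scenarios, all upward after 12 months):

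| Month | Bias, percentage points |
|---|---|
| 12 | 0.0 |
| 15 | +0.4 to +0.7 |
| 18 | +1.2 to +2.2 |
| 24 | +2.6 to +5.7 |
| 30 | +3.2 to +9.0 |

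Two examples, both with frailty variance 0.5:

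- Medians 4 and 6 months: true 24-month OS 31.7%, Kaplan-Meier 36.0%.
- Medians 3 and 8 months: true 18- and 24-month OS 44.2% and 34.3%, Kaplan-Meier about 46.5% and 40.0%. Median OS is 15.3 months, read as 15.9.

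*Other dependence (Gaussian copula, exponential R), bias at 24 months:* correlation 0, +0.2 to +3.5; 0.3, +1.7 to +6.7; 0.6, +3.3 to +11.4.

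*When the sign changes.* The bias vanished or reversed when D and R were independent and either the hazard after stopping fell steeply (Weibull shape 0.75 or below) or 20% stopped early for toxicity and then lived longer. With medians of 4 and 6 months, and toxicity stops followed by three times longer survival, true 24-month OS of 21.2% is read as 19.8%. Adding a falling hazard (shape 0.6) gives 31.6% read as 27.5%, or −4.1 points. With medians of 2 and 5 months, 1.5 times longer survival is enough: 7.1% read as 6.5%.

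**Sampling error.** For the 3- and 8-month example with n = 30, the standard deviation of the Kaplan-Meier estimate is about 9.8 points at 18 months and 10.8 at 24, against biases of about 2.4 and 5.8. About 4 of 30 patients remain at risk at 24 months.

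**After the fix.** With a common cut-off giving each patient an assumed 30 to 48 months of potential follow-up whatever the stopping date, the bias is 0.0 at 12 to 30 months in all 24 shared-frailty scenarios.

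**The case against.** The strongest objection is to the direction. A reader might infer that the curve is certain to be biased upward. The documents do not support that. Section 5.3 also lists toxicity, intercurrent illness and patient choice, and sections 5.5 and 6.1 remove patients for vascular occlusive events without progression. The trial of ponatinib in gastrointestinal stromal tumour, summarised in section 2.2.1, suggests that such stops need not be rare. Seven patients discontinued for adverse events, most after less than two weeks on drug. With 19 patients reported as 54.3%, N is about 19 / 0.543 = 35, so 7 / 35 = 20%. If these patients outlive the others and prognosis is not otherwise shared, the sign reverses. This stands and limits the claim to a likely direction.

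It also stands that the size rests on assumed medians, that noise at this sample size often exceeds the bias, and that section 12.4 promises no OS landmark, test or target. None of this removes the problem: a confidence interval does not correct a systematic shift.

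A reader might also take OS to be a formal endpoint of both cohorts. Section 1.2 names no cohort, and section 12.2 describes Cohort B as exploratory, without specific endpoints. What section 12.4 does plan is a curve for each cohort.

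**Conclusion.** The point holds in a conditional form. Followed exactly, the plan makes OS censoring after about 12 months from first dose depend on time on treatment, and so on prognosis. Where early stopping signals shorter survival, the later curve is too high, by roughly 1 to 2 points at 18 months and 3 to 6 at 24 in most shared-prognosis scenarios. Stronger dependence gives more, up to 11.4 points at 24 months in the scenarios run. These sizes depend wholly on the assumed medians and the form of dependence.

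The rule does not affect OS up to 12 months, a median OS below about 12 months, or the response-rate decision in section 12.2. This is a low-priority improvement to a descriptive secondary analysis. It would matter mainly if 18- or 24-month OS, or a median well beyond a year, were reported without a caveat.

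**What to change.** Preferred: amend section 5.4, footnote 9 of section 10, and section 12.4 so that vital status is ascertained for every patient, whatever the date of stopping, either to one common data cut-off or to the same time from first dose. A telephone or record check is enough, and footnote 9 already allows telephone contact once toxicity has resolved. The cost is a few extra contacts per surviving patient.

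If that is not done, add a sentence to section 12.4 with one of two statements:

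- OS estimates and curves are reported only to 12 months from first dose. This needs no new data, but later data on long-term responders are not used for OS.
- Later portions are shown with numbers at risk and flagged as subject to informative censoring. This costs only wording, but it warns of the bias without removing it.

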5.5 Criteria for Removal from Study

Patients will be removed from study when any of the criteria listed in **Section 5.3** applies. The reason for study removal and the date the patient was removed must be documented in the Case Report Form.

Patients must be discontinued from the trial in the event of myocardial infarction, stroke,

development or progression of arterial disease necessitating revascularization, or other vascular occlusive events.

6. DOSING DELAYS/DOSE MODIFICATIONS

6.1 Dose Modifications for Ponatinib

A maximum of two ponatinib dose level reductions are allowed. If a third dose level reduction is required, treatment will be permanently discontinued. The starting dose for ponatinib is 45 mg oral daily.

Patients who experience a vascular (arterial or venous) occlusive event should be immediately discontinued from the study and ponatinib should not be restarted. For serious reactions other than arterial or venous occlusion, do not restart until the serious event has resolved.

Dose Modifications

Dose Level	Ponatinib Dose/Schedule
0	45 mg daily
-1	30 mg daily
-2	15 mg daily

Dose Modification for Nausea

Nausea and vomiting are reported with ponatinib. The use of an antiemetic prophylactically is not recommended. However, if a patient is symptomatic, appropriate antiemetic medications may be used as clinically indicated.

CTCAE Grade	Action and Dose Modification
≤ Grade 1	No change in dose
Grade 2	Occurrence at 45 mg: 
• Interrupt ponatinib and resume at 45 mg after recovery to ≤ Grade 1 Occurrence at 30 mg: 
• Interrupt ponatinib and resume at 30 mg after recovery to ≤ Grade 1 Occurrence at 15 mg: 
• Discontinue ponatinib
Grade 3	Occurrence at 45 mg: 
• Interrupt ponatinib and resume at 30 mg after recovery to ≤ Grade 1 Occurrence at 30 mg: 
• Interrupt ponatinib and resume at 15 mg after recovery to ≤ Grade 1 Occurrence at 15 mg: 
• Discontinue ponatinib
Grade 4	Off protocol therapy

**Patients requiring > two dose reductions should go off protocol therapy.*

Recommended management: Anti-emetics.

Dose Modification for Vomiting

CTCAE Grade	Action and Dose Modification
≤ Grade 1	No change in dose
Grade 2	Occurrence at 45 mg: • Interrupt ponatinib and resume at 45 mg after recovery to ≤ Grade 1 Occurrence at 30 mg: • Interrupt ponatinib and resume at 30 mg after recovery to ≤ Grade 1 Occurrence at 15 mg: Discontinue ponatinib
Grade 3	Occurrence at 45 mg: • Interrupt ponatinib and resume at 30 mg after recovery to ≤ Grade 1 Occurrence at 30 mg: • Interrupt ponatinib and resume at 15 mg after recovery to ≤ Grade 1 Occurrence at 15 mg: Discontinue ponatinib
Grade 4	Off protocol therapy

*Patients requiring > two dose reductions should go off protocol therapy.

Recommended management: Anti-emetics.

Dose Modification for Diarrhea

Diarrhea is a common side effect of ponatinib. The use of anti-diarrheal medications is permitted. Patients who experience ≥ grade 2 diarrhea may begin loperamide (4 mg orally x 1, then 2 mg orally after each loose stool).

CTCAE Grade	Action and Dose Modification
≤ Grade 1	No change in dose
Grade 2	Occurrence at 45 mg: • Interrupt ponatinib and resume at 45 mg after recovery to ≤ Grade 1 Occurrence at 30 mg: • Interrupt ponatinib and resume at 30 mg after recovery to ≤ Grade 1 Occurrence at 15 mg: Discontinue ponatinib
Grade 3	Occurrence at 45 mg: • Interrupt ponatinib and resume at 30 mg after recovery to ≤ Grade 1 Occurrence at 30 mg: • Interrupt ponatinib and resume at 15 mg after recovery to ≤ Grade 1 Occurrence at 15 mg: Discontinue ponatinib
Grade 4	Off protocol therapy

CTCAE Grade	Action and Dose Modification
**Patients requiring > two dose reductions should go off protocol therapy.	Recommended management: Loperamide antidiarrheal therapy Dosage schedule: 4 mg at first onset, followed by 2 mg with each loose motion until diarrhea-free for 12 hours. Adjunct antidiarrheal therapy is permitted and should be recorded when used.

Dose Modifications for Hepatic Toxicity

Hepatotoxicity, most commonly manifested by reversible transaminase and alkaline phosphatase elevation and hyperbilirubinemia, has been observed in patients taking ponatinib. Monitoring of hepatic function is recommended and management of laboratory abnormalities should be managed with dose interruption and/or dose reduction according to the dose modification table.

CTCAE Grade	Action and Dose Modification
Elevation of liver transaminases > 3 x ULN* or alkaline phosphatase > 2.5 x ULN (Grade 2 or higher; or alkaline phosphatase > 4x ULN if related to metastatic disease limited to liver [e.g. cholangiocarcinoma])	
Occurrence at 45 mg:
 
 • Interrupt ponatinib and monitor hepatic function • Resume ponatinib at 30 mg after recovery to ≤ Grade 1 (< 3 × ULN) 
Occurrence at 30 mg:
 
 • Interrupt ponatinib and resume at 15 mg after recovery to ≤ Grade 1 
Occurrence at 15 mg:
 
 • Discontinue ponatinib
Elevation of AST or ALT ≥ 3 x ULN concurrent with an elevation of bilirubin > 2 x ULN and alkaline phosphatase > 2 x ULN	Discontinue ponatinib

Dose Modifications for Myelosuppression

While myelosuppression can occur any time during treatment, its onset most commonly occurs within the first month on treatment. Ponatinib has not been studied in solid tumor patients and whether (or to what extent) myelosuppression will occur in these patients is unknown.

	Action and Dose Modification
Absolute Neutrophil Count (ANC) < 1 x 10 ⁹ /L Or Platelets < 50 x 10 ⁹ /L	
First Occurrence
 
 • Interrupt ponatinib and resume initial dose after recovery to ANC ≥ 1.5 x 10⁹/L and platelet ≥ 75 x 10⁹/L 
Second Occurrence
 
 • Interrupt ponatinib and resume at 30 mg after recovery

	Action and Dose Modification
	
to ANC $\geq 1.5 \times 10^9/L$ and platelet $\geq 75 \times 10^9/L$
 
Third Occurrence
 
 • Interrupt ponatinib and resume at 15 mg after recovery to ANC $\geq 1.5 \times 10^9/L$ and platelet $\geq 75 \times 10^9/L$

Dose Modifications for Hemorrhage

Concomitant use of ponatinib with anticoagulants should be approached with caution in patients who may be at risk of bleeding events. Serious bleeding events, including fatalities have been reported in patients treated with ponatinib. Most hemorrhagic events, but not all, occurred in patients with grade 4 thrombocytopenia. Interrupt ponatinib for serious or severe hemorrhage and evaluate.

CTCAE Grade	Action and Dose Modification
Grade 1	No intervention
Grade 2	
Occurrence at 45 mg:
 
 • Interrupt ponatinib and resume at 30 mg after recovery to \leq Grade 1 
Occurrence at 30 mg:
 
 • Interrupt ponatinib and resume at 15 mg after recovery to \leq Grade 1 
Occurrence at 15 mg:
 
 • Discontinue ponatinib
Grade 3 or 4	Permanently discontinue ponatinib

Dose Modifications for Pancreatitis / Lipase Elevations

Pancreatitis (symptomatic abdominal pain associated with pancreatic enzyme elevation) and/or elevations in lipase and amylase are known AEs associated with ponatinib. Most cases of pancreatitis or elevated pancreatic enzymes occur within the first 2 months of treatment with ponatinib. Patients with low-grade (1 or 2) elevation in enzymes can be continued without dose reduction but should be monitored closely with serial enzyme level determinations. Patients can continue with ponatinib treatment at the same or a reduced dose once the event has improved to grade 1 or resolved. See below for dose-modification guidelines.

CTCAE Grade	Action and Dose Modification
Asymptomatic Grade 1 or 2 elevation of serum lipase	Consider interruption or dose reduction of ponatinib
Asymptomatic Grade 3 or 4 elevation of lipase ($> 2 \times$ ULN*) or asymptomatic radiologic pancreatitis (Grade 2 pancreatitis)	
Occurrence at 45 mg:
 
 Interrupt ponatinib and resume at 30 mg after recovery to \leq Grade 1 ($< 1.5 \times$ ULN) 
Occurrence at 30 mg:
 
 Interrupt ponatinib and resume at 15 mg after recovery to \leq Grade 1 
Occurrence at 15 mg:
 
 Discontinue ponatinib
Symptomatic Grade 3 pancreatitis	
Occurrence at 45 mg:
 
 Interrupt ponatinib and resume at 30 mg after complete resolution of symptoms and after recovery of lipase elevation to \leq Grade 1 
Occurrence at 30 mg:
 
 Interrupt ponatinib and resume at 15 mg after complete resolution of symptoms and after recovery of lipase elevation to \leq Grade 1 
Occurrence at 15 mg:
 
 Discontinue ponatinib
Grade 4 pancreatitis ($> 5 \times$ ULN of lipase)	Discontinue ponatinib

*ULN = Upper Limit of Normal for the lab

Dose Modifications for Skin Rash

Skin rashes have been commonly reported in patients taking ponatinib. The vast majority of the skin events are nonserious, either self-limiting or manageable with antihistamines or topical steroids, and do not result in discontinuation. In more severe cases, a short course of oral corticosteroids may be used until the rash has improved or resolved. In patients treated with ponatinib, the most common skin manifestations are a diffuse maculopapular rash that is non-pruritic or an acneiform dermatitis. Occasionally, patients treated with ponatinib have been reported to have a dry, flaky or exfoliative type of rash or psoriasiform dermatitis. Rarely, an erythema multiforme type of rash has been associated with ponatinib.

CTCAE Grade	Action and Dose Modification
Grade 2 persistent* despite optimal symptomatic therapy, but not clinically significant	No change, continue ponatinib therapy, continue monitor every 2 weeks.

CTCAE Grade	Action and Dose Modification
Grade 2 persistent* despite optimal symptomatic therapy, is clinically significant	
Hold ponatinib
 
Resume at 45 mg after recovery to \leq grade 1
 
Recurrence at 45 mg: Hold ponatinib
 
Resume at 30 mg after recovery to \leq grade 1
 
Recurrence at 30 mg: Hold ponatinib
 
Resume at 15 mg after recovery to \leq grade 1
 
Recurrence at 15 mg: Discontinue ponatinib

Grade 3 persistent* despite optimal symptomatic therapy, but not clinically significant	
No change, continue ponatinib therapy, continue monitor every 2 weeks.

Grade 3 persistent* despite optimal symptomatic therapy, is clinically significant	
Hold ponatinib
 
Resume at 30 mg after recovery to \leq grade 1
 
Recurrence at 30 mg: Hold ponatinib
 
Resume at 15 mg after recovery to \leq grade 1
 
Recurrence at 15 mg: Discontinue ponatinib

*Persistent rash is defined as 7 days.

Guidelines for Supportive Care of Rash	
Type of Care	Action
Prevention/Prophylaxis	
 Avoid unnecessary exposure to sunlight. Apply broad-spectrum sunscreen (containing titanium dioxide or zinc oxide) with a skin protection factor (SPF) ≥ 15 at least twice daily. Use thick, alcohol-free emollient cream (e.g., glycerine and cetomacrogol cream) on dry areas of the body at least twice daily.
Symptomatic Care ^a	
 Pruritic lesions: Cool compresses and oral antihistamine therapies. Fissuring lesions: Monsel's solution, silver nitrate, or zinc oxide cream. Desquamation: Thick emollients and mild soap. Paronychia: Antiseptic bath, local potent corticosteroids in addition to antibiotics; if no improvement, consult dermatologist or surgeon. Infected lesions: Appropriate bacterial/fungal culture-driven systemic or topical antibiotics.

Guidelines for Supportive Care of Rash	
Type of Care	Action
a Patients who develop rash/skin toxicities should be seen by a qualified physician and should receive evaluation for symptomatic/supportive care management.	

Dose Modifications for Hypertension

Patients receiving ponatinib have experienced hypertension and blood pressure should be monitored at each visit. In subjects with an initial BP reading within the hypertensive range, a second reading should be taken at least 2 minutes later, with the two readings averaged to obtain a final BP measurement. The averaged value should be recorded in the eCRF.

For patients who develop HTN or worsening HTN during study treatment, antihypertensive medication should be initiated or optimized to achieve target blood pressure before interruption or dose reduction of the study treatment at the discretion of the investigator. If hypertension is persistent despite adequate anti-HTN therapy including titration of anti-HTN medication or introduction of additional anti-HTN medications, or if grade 4 HTN develops, dose interruption, reduction or discontinuation is recommended. Patients with prior history of hypertension (on anti-hypertensive agents) should monitor/record their BP at home while on ponatinib therapy. Patients will be provided with a diary to record their at-home assessments.

Patients will obtain blood pressure assessments twice per week at home, using a blood pressure cuff supplied by Takeda for purposes of the research study. Any reading within the hypertensive range will be confirmed in clinic.

Event	Management Guideline	Dose Modification
Definitions used in the table:		
	
 - Persistent hypertension: Hypertension detected in two separate readings during up to three subsequent visits. - Well-controlled hypertension: Blood pressure of SBP \leq140 mmHg and DBP \leq90 mmHg in two separate readings during up to three subsequent visits. - Symptomatic hypertension: Hypertension associated with symptoms (e.g., headache, lightheadedness, vertigo, tinnitus, episodes of fainting) that resolve after the blood pressure is controlled within the normal range. - Asymptomatic hypertension: SBP $>$140 mmHg and/or DBP $>$90 mmHg in the absence of the above symptoms. 	

Event	Management Guideline	Dose Modification
(Scenario A) 
 Asymptomatic and persistent SBP of ≥ 140 and < 160 mmHg, or DBP ≥ 90 and < 100 mmHg, or Clinically significant increase in DBP of 20 mmHg (but still below 100 mmHg). 	
 Adjust current or initiate new antihypertensive medication(s). Titrate antihypertensive medication(s) during the next 2 weeks to achieve well-controlled BP. If BP is not well-controlled within 2 weeks, consider referral to a specialist and go to scenario (B). 	Continue ponatinib at the current dose.
(Scenario B) 
 Asymptomatic SBP ≥ 160 mmHg, or DBP ≥ 100 mmHg, or Failure to achieve well-controlled BP within 2 weeks in Scenario A. 	
 Adjust current or initiate new antihypertensive medication(s). Titrate antihypertensive medication(s) during the next 2 weeks to achieve well-controlled BP. 	
 Interrupt ponatinib. Once BP is well-controlled, restart ponatinib at a reduced dose.
(Scenario C) 
 Symptomatic hypertension or Persistent SBP ≥ 160 mmHg, or DBP ≥ 100 mmHg, despite antihypertensive medication and dose reduction of study treatment 	
 Adjust current or initiate new antihypertensive medication(s). Titrate antihypertensive medication(s) during the next 2 weeks to achieve well-controlled BP. Referral to a specialist for further evaluation and follow-up is recommended. 	
 Interrupt ponatinib. Once BP is well-controlled, restart ponatinib at a reduced dose.
(Scenario D) Refractory hypertension unresponsive to above interventions or hypertensive crisis.	Continue follow-up per protocol.	Discontinue ponatinib.

Dose Modifications for Ocular Toxicity

Ocular toxicities have occurred in clinical trials of ponatinib. Serious ocular toxicities leading to blindness or blurred vision have occurred in ponatinib-treated patients. Patients are required to have a standard ophthalmic exam performed by an ophthalmologist at baseline and as clinically warranted. The exam will include indirect fundoscopic examination, visual acuity (corrected), visual field examination, tonometry, and direct fundoscopy.

Retinal toxicities including macular edema, retinal vein occlusion, and retinal hemorrhage have occurred in ponatinib-treated patients.

Grade	Management Guideline	Dose Modification
Grade 1 Asymptomatic or symptomatic but not limiting ADL; intervention not indicated.	
 Consult ophthalmologist within 7 days of onset. Exclude ME, RVO, or RH. Consult retinal specialist if available in case of ME, RVO, or RH Continue follow up examination(s) (by retinal specialist if available) for ME, RVO, or RH 	
 Continue ponatinib at the same dose level until ophthalmologic examination can be conducted.* If ophthalmologic examination cannot be performed within 7 days of onset, interrupt ponatinib until ME, RVO, or RH can be excluded and symptoms resolve. If ME, RVO, or RH excluded restart ponatinib at same dose level. If ME: Permanently discontinue ponatinib. If RVO: Permanently discontinue ponatinib. If RH: Permanently discontinue ponatinib.
Grade 2 and 3 Grade 2 defined as: Symptomatic with moderate decrease in visual acuity (20/40 or better; limiting instrumental ADL; local or non-invasive intervention indicated. Grade 3 defined as: Symptomatic with marked decrease in visual acuity or marked visual field defect (worse than 20/40 but better than 20/200); severe pain or medically significant; operative intervention indicated.	
 Consult ophthalmologist immediately. Exclude ME, RVO, or RH. Consult retinal specialist in case of ME, RVO, or RH for follow-up exam. Continue follow up examination(s) (by retinal specialist if available) for ME, RVO, or RH. 	
 Interrupt ponatinib until signs and symptoms have resolved to baseline. If ME, RVO, or RH excluded and symptoms resolved to baseline, restart ponatinib reduced by one dose level. If ME: Permanently discontinue ponatinib. If RVO: Permanently discontinue ponatinib. If RH: Permanently discontinue ponatinib.
